#### Pharmacology/Pharmacokinetic Studies

Pharmacokinetic studies in adults in the Topalian study showed a median time to peak concentration of 1-4 hours after the start of the one hour infusion and a dose proportion increase in peak concentration and area under the curve with increasing dose across the dose range 0.1 mg/kg-10 mg/kg. Half-life is 2-4 weeks, similar to other therapeutic antibodies. Minimum concentrations 15 days after the first dose 3 mg/kg of Nivolumab from 34 adults treated on CA209003 are shown in Table 2. Based upon this, the pediatric trial will seek to target a minimum exposure of 10 mcg/ml.

Table 2. Trough Nivolumab Concentrations in Adults
---

Percentile	Cmin (mcg/ml)
Min	6.9
5	8.9
10	11.0
15	11.3
20	12.4
25	13.0
30	14.3
35	15.0
40	17.0
45	17.2
50	17.6
55	18.0
60	19.9
65	21.0
70	22.1
75	24.1
80	24.5
85	25.4
90	28.6
95	31.2
Max	38.1

Pharmacodynamic analysis of PD-1 receptor occupancy revealed 64-70% occupancy across the range of dose levels tested. Tumors were analyzed for PD-L1 expression from archival samples in 42 patients. Of these, samples from 25 patients showed PD-L1 expression by immunohistochemical analysis (cutoff for positivity being > 5% of cells expressing PD-L1). Responses were observed in 9/25 patients with PD-L1 expression by IHC, whereas 0/17 patients without PD-L1 expression showed antitumor responses with anti-PD1 therapy. More recent data from Grosso and colleagues assessed objective response rates to nivolumab in patients with melanoma using a cutoff of 5% PD-L1 expression. In this study, 14% of patients with PD-L1 negative tumors had objective antitumor responses compared to 41% of patients with PD-L1+ tumors.

In summary, anti-PD1 mAbs demonstrate response rates of 30-50% in patients with melanoma and 20-30% in patients with renal cell carcinoma and non-small cell lung cancer. Toxicities associated with checkpoint inhibition are primarily limited to autoimmune reactions. These occur in approximately 30% of adults and children treated with anti-CTLA4, but in <10% of patients treated with anti-PD1. Thus, compared to anti-

CTLA4, anti-PD1 based checkpoint inhibitors demonstrate more potent antitumor effects across a wider range of histologies, with less toxicity. Preliminary studies in adults have demonstrated higher response rates in patients with tumors expressing of the PD-L1, the major ligand for PD1, although antitumor responses have also been seen in patients with PD-L1 negative tumors. Thus, there is currently no accurate biomarker to predict tumor response to anti-PD1 therapy. In a single arm, non-randomized study, combination therapy with anti-PD1 plus anti-CTLA4 resulted in higher response rates for metastatic melanoma than observed with either agent alone, with a similar toxicity profile to that observed with anti-CTLA4 mAb therapy. Preclinical studies have demonstrated antitumor effects of anti-PD1 in a murine model of rhabdomyosarcoma, but there is currently limited information about PD-L1 expression in pediatric tumors.

## 2.4 Pediatric Studies

### Prior Experience in Children

A pediatric Phase I trial of ipilimumab, sponsored by CTEP and led by the Pediatric Oncology Branch of the NCI is nearing completion. Ipilimumab was administered to patients 2-21 years old with refractory solid tumors. Dose cohorts included 1, 3, 5, and 10 mg/kg IV in a standard 3 + 3 design with 4 doses of induction therapy every 3 weeks followed by maintenance every 3 months until disease progression or unacceptable toxicity. Tumors were measured after 6 weeks, 12 weeks, and then every 3 months. Thirty patients with pediatric solid tumors (melanoma n=10, osteosarcoma n=8, soft tissue sarcomas n=7, renal malignancies n=3 and neuroblastoma n=2) have been enrolled. Subjects >12 years of age tolerated the highest dose of 10 mg/kg tested. For subjects < 12 years of age, 3 mg/kg was tolerated without DLT, however DLT was observed in 2 subjects < 12 years treated at 10 mg/kg. In children < 12 years, the MTD was 5mg/kg. Grade 3/4 immune related adverse events (IrAE) included colitis (3) transaminitis (2), autoimmune thyroiditis (1), pancreatitis (1), and hypophysitis (1). Except for a lesser incidence of rash, this frequency and spectrum of IrAE appears similar to that observed in adults treated with ipilimumab. IrAE developed as early as week 1 and as late as 36 weeks, but the majority occurred in the first three weeks. Confirmed stable disease (stable disease at both 6 and 12 week scans) was the best response in 5 patients with melanoma, clear cell sarcoma or osteosarcoma, with a duration of 3 -18 months. Pharmacokinetics revealed no significant differences related to age and the exposure to ipilimumab in children was essentially the same as that for adults given the equivalent mg/kg dose. Although this study raises the prospect that younger children may have lesser tolerance to anti-CTLA4 therapy as compared to adolescents, this is based upon very small numbers and may not be truly related to differences in biology.

We have demonstrated tolerability of the combination at nivolumab 3 mg/kg and ipilimumab 1 mg/kg in Part C. An open question remains if the combination dosing is optimal as delivered in Part D. Reports have suggested improved efficacy at a higher ipilimumab dose. Antonia et al. demonstrated tolerability and potential survival benefit in patients treated with 1 mg/kg nivolumab in combination with 3 mg/kg ipilimumab in patients with small cell lung cancer. Other studies at this dose combination are ongoing. In order to test this dose combination, we will test in Part E and limit to children with rhabdomyosarcoma or Ewing sarcoma/Peripheral PNET. The rationale for including children with rhabdomyosarcoma is that in Part D, out of all the histologic cohorts treated with

combination, we observed one PR to the combination at the Part D dose in a patient with rhabdomyosarcoma. Thus, we will test the combination of nivolumab (1 mg/kg) with ipilimumab (3 mg/kg) to determine if the increased dose of ipilimumab demonstrates improved efficacy in a cohort of pediatric patients with rhabdomyosarcoma or Ewing sarcoma/Peripheral PNET.

## 2.5 Overview of Proposed Pediatric Study

Initially the study opened with 3 parts (Part A, Part B, and Part C) and has been amended to add parts D and E.

Part A will aim to define the recommended phase 2 dose (RP2D), which is a tolerable dose of nivolumab that provides systemic exposure similar to that achieved by the RP2D in adults. The goal of Part A will be to enroll at least 6 children with recurrent or refractory solid tumors, excluding CNS tumors. Patients enrolled on Part A must have measurable or evaluable disease. Part A will enroll at 3 mg/kg nivolumab every 14 days until disease progression or until toxicity requires treatment discontinuation. A cycle will be considered 28 days (2 doses) and the DLT monitoring period will be 28 days. Patients will be monitored for toxicity using standard CTCAE v.5 criteria. If DLT is observed in 2 or greater patients, the dose will be de-escalated to 1 mg/kg every 2 weeks and an additional cohort will be evaluated for toxicity and exposure at that dose level.

Part A will seek to ascertain that children treated at the 3 mg/kg dose (or 1 mg/kg dose if de-escalation occurs) do not experience significantly less drug exposure than adults treated at the 3 mg/kg dose level. [Table 2](#) demonstrates the 95% confidence interval for nivolumab Cmin after the first dose is approximately 10-30 mcg/ml. Therefore, Cmin levels for patients treated in Part A will be evaluated prior to initiation of Part B. If at least 5 of 6 patients achieve a Cmin of at least 10 mcg/ml, we will conclude that children are not experiencing significantly less exposure than adults treated at the same dose. If however, < 5 of 6 patients achieve a Cmin of at least 10 mcg/ml, consideration will be given to a protocol amendment to test a higher dose level in Part A. Note that Cmin levels > 30 mcg/ml will not, in and of itself result in a change in protocol design, unless excess toxicity is observed.

Except for patients with neuroblastoma and MIBG only disease, response assessment will use standard RECIST criteria. Determination of progression will use target selection and single dimension measurements according to RECIST criteria. Patients will be removed from study if tumor size increases from baseline in target lesions selected according to RECIST criteria. However, because a minority of subjects treated with immunotherapy may derive clinical benefit despite initial evidence of progressive disease (e.g. pseudoprogression) patients will be allowed to remain on study if the magnitude of increase in tumor size is <40% and the bulleted criteria below are met. Patients who develop a new lesion while on study are eligible to remain on study if they meet the criteria bulleted below and the sum of the total tumor burden remains < 40% according to RECIST criteria. These are adapted from similar criteria already in place in trials of checkpoint inhibitors in adults with cancer and have been utilized in the Phase I trial of ipilimumab in children. Additional criteria required in order to allow a patient to remain on study despite an increase in tumor size of > 20% but < 40% are the following:

- In the judgment of the treating clinician, the patient does not show evidence for rapid disease progression and/or the patient has shown evidence for clinical benefit.

- There is no decrease in performance status.
- The patient is tolerating the study drug and has not experienced a DLT.
- Continued treatment with nivolumab alone or in combination with ipilimumab will not delay an imminent intervention required to prevent a serious complications (e.g. CNS metastases which require radiation therapy or surgery).

For patients who remain on study despite increase in tumor size of > 20%, imaging to include target lesions must occur following every cycle if clinically indicated, and the same radiographic and clinical criteria must be met in order to remain on study. If tumor size subsequently diminishes to < 20% increase from baseline, the patient may be followed according to the standard protocol guidelines which will involve less frequent imaging. The decision to continue treatment beyond radiographic evidence for disease progression should be discussed with the Study Chair and/or her designee and documented in the study record.

Response for patients with MIBG only neuroblastoma will be assessed according to [Section 12.4.2](#).

Once a RP2D is identified in Part A, an expansion cohort of up to 6 additional patients will be treated at the nivolumab monotherapy RP2D to acquire PK data in a representative number of young patients (i.e. 6 patients < 12 years of age and 6 patients  $\geq$  12 years).

Twelve evaluable patients were enrolled to Part A (June 2017). None had dose limiting toxicity, the RP2D of single agent nivolumab was determined to be 3 mg/kg IV q14 days. Pharmacokinetic parameters were similar to adults. In children (n=11), the nivolumab Cmax (n=11) was  $63.2 \pm 15.7$  mg/mL, half-life was  $10.7 \pm 1.8$  days and clearance was  $0.196 \pm 0.075$  mL/h/kg.

Part B and Part C will open simultaneously. Part B will evaluate the activity of nivolumab at its RP2D in expanded cohorts with the goal of enrolling at least 10 patients per tumor type: neuroblastoma, osteosarcoma, rhabdomyosarcoma, Ewing sarcoma, Hodgkin lymphoma, and non-Hodgkin lymphoma. Measurable disease is required for enrollment on Parts B1-B6, measurable or evaluable disease is required for Part B7 (melanoma) and MIBG evaluable disease without measurable disease in patients with neuroblastoma (Part B8). Patients aged 1-30 years may enroll on Parts B1-B6, B8; patients < 18 years may enroll on Part B7. The primary objective of Part B is to identify histologic subtypes where there is a signal for anti-tumor activity, using a Simon's optimal two-stage design, with the exception of Part B7, which will serve as a non-statistical access cohort (without minimum or maximum accrual limits) for the rare diagnosis of melanoma, to remain open to enrollment until Parts B1-B6, B8 are complete. Note that patients who have an initial increase in target lesions but eventually show a response according to RECIST criteria will be considered responders for the purpose of defining response in Cohort B. Parameters for response and progression are measured in relation to baseline measurements.

Preliminary data from Part B (June 2017, nivolumab 3 mg/kg every 14 days) for osteosarcoma (n=10), Ewing sarcoma (n=10), and rhabdomyosarcoma (n=10) was presented at ASCO 2017. There were no objective responses. Enrollment to first stage of Hodgkin lymphoma, neuroblastoma measurable disease, and neuroblastoma MIBG evaluable disease cohorts is completed and response assessment pending.

Part C will aim to enroll at least 15 patients with the same eligibility criteria required for

enrollment on Part A, with the goal of identifying the MTD or RP2D of the combination of nivolumab plus ipilimumab. The first dose level will be nivolumab at 1 mg/kg and ipilimumab at 1 mg/kg with the goal of enrolling at least 3 patients at this dose level, with both agents administered every three weeks x 4 followed by nivolumab 3 mg/kg every 2 weeks until disease progression or toxicity. The second dose level will be nivolumab at 3 mg/kg and ipilimumab at 1 mg/kg on the same schedule, with the goal of enrolling at least 12 patients at this dose level. An expansion cohort of up to 6 additional patients will be treated at the nivolumab/ipilimumab combination RP2D to acquire PK data in a representative number of young patients (i.e. 6 patients < 12 years of age and 6 patients ≥ 12 years in Part C). If dose level 1 is not tolerated due to toxicity there will be no de-escalated dose studied.

Except for patients with neuroblastoma and MIBG only disease, response assessment will use standard RECIST, with the caveats regarding pseudo-progression noted above. Patients with primary brain tumors or active CNS metastases will be excluded from this trial due to concerns regarding pseudo-progression in the CNS. Patients with a history of CNS metastases that have been previously treated may enroll if sequential imaging shows no evidence for active disease. Patients with extra axial disease [e.g. skull (bone) metastasis that do not invade the dura] may enroll if there is no evidence for CNS edema associated with the lesion. Patients on systemic corticosteroids and/or with a history of autoimmunity or previous allogeneic stem cell transplant will also be excluded. Management of autoimmune toxicities will be guided by algorithms ([Appendix VIII](#)) developed for nivolumab in adults and for ipilimumab in children with cancer, where autoimmune toxicity was also observed.

In Part C (June 2017) of the study, five evaluable patients enrolled at dose level 1 (nivolumab 1 mg/kg) in combination with ipilimumab (1 mg/kg), none had dose limiting toxicity. At dose level 2, nivolumab (3 mg/kg) in combination with ipilimumab (1 mg/kg), twelve patients were evaluable and one had grade 2 creatinine elevation that met criteria for dose limiting toxicity. Part C has demonstrated that nivolumab (3 mg/kg) in combination with ipilimumab (1 mg/kg) is tolerated in children and adolescents.

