**1.0 GOALS AND OBJECTIVES (SCIENTIFIC AIMS)****1.1 Primary Aims**

Determine the tolerability, and define and describe the toxicities of nivolumab administered as a single agent in children with relapsed or refractory solid tumors at the adult recommended dose of 3 mg/kg.

Determine if systemic nivolumab exposure in children is similar to the systemic exposure in adults following a 3 mg/kg dose.

Determine the maximum tolerated dose (MTD) and/or recommended Phase 2 dose (RP2D) and define and describe the toxicities of nivolumab plus ipilimumab administered to children with relapsed or refractory solid tumors.

Assess antitumor effects of nivolumab across selected childhood solid tumors in seven expansion cohorts (Parts B1-B6, B8); neuroblastoma (2 cohorts: measurable disease; MIBG positive only non-measurable disease), osteosarcoma, rhabdomyosarcoma, Ewing sarcoma, Hodgkin lymphoma, and non-Hodgkin lymphoma. A non-statistical access cohort for the rare diagnosis of melanoma (Part B7) will remain open to enrollment until Parts B1-B6, B8 are complete B7 to preliminarily define the antitumor effects of nivolumab within the confines of a phase 1/2 study.

Assess antitumor effects of nivolumab in combination with ipilimumab across selected childhood solid tumors in two dose combinations (Part D and Part E).

Characterize the pharmacokinetics of nivolumab alone and in combination with ipilimumab, including AUC, Cmax, Cmin, using intensive sampling.

Assess immunogenicity of nivolumab alone and in combination with ipilimumab by measuring anti-drug antibody (ADA) levels

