### 11.3 Determination of Recommended Phase 2 Dose for Nivolumab as a Single Agent (Part A):

- Part A will evaluate a single dose level (3 mg/kg). If 1 or fewer of 6 evaluable patients experience DLT and at least 5/6 of patients achieve a Cmin of at least 10 mcg/ml, the 3 mg/kg dose level will be the RP2D and we will conclude that children are not experiencing significantly less exposure than adults treated at the same dose. If however, < 5 of 6 patients achieve a Cmin of at least 10 mcg/ml, consideration will be given to a protocol amendment to test a higher dose level in Part A. Note that Cmin levels > 30 mcg/ml will not, in and of itself result in a change in protocol design, unless excess toxicity is observed.
- If 2 or more of the 6 patients experience DLT at the 3 mg/kg dose level, then the MTD has been exceeded and the 1 mg/kg dose level will be evaluated. If 1 or fewer of 6 patients experience DLT at the 1 mg/kg dose level and at least 5/6 of patients achieve a Cmin of at least 10 mcg/ml, then this dose level will be the RP2D. Once the RP2D for nivolumab as a single agent is determined, Part B and Part C will open simultaneously.

Update: The single-agent recommended Phase 2 dose of Part A was determined to be 3 mg/kg nivolumab.

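### The primary aim on child versus adult nivolumab exposure has no analysis that can show similarity: the 5-of-6 trough gate supports only 'not less', and the reported similarity is not documented by the comparators shown

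*Combined protocol and SAP*

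**What the plan says.** Section 1.1 lists as a primary aim: "Determine if systemic nivolumab exposure in children is similar to the systemic exposure in adults following a 3 mg/kg dose". The abstract and section 2.5 also define the single-agent recommended phase 2 dose partly by exposure similar to that in adults.

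The only exposure criterion is in 2.5 and 11.3. Given an acceptable DLT count, if "at least 5/6 of patients achieve a Cmin of at least 10 mcg/ml, the 3 mg/kg dose level will be the RP2D". When it is met, "we will conclude that children are not experiencing significantly less exposure than adults treated at the same dose". Troughs above 30 mcg/ml "will not, in and of itself result in a change in protocol design, unless excess toxicity is observed".

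The threshold comes from section 2.3: "Minimum concentrations 15 days after the first dose 3 mg/kg of Nivolumab from 34 adults treated on CA209003 are shown in Table 2". Section 2.5 says that this table "demonstrates the 95% confidence interval for nivolumab" Cmin, at about 10 to 30 mcg/ml.

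For pharmacokinetics, section 11.9 plans means, medians, ranges and standard deviations. It gives no margin, ratio, interval or comparison with adults.

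The June 2017 update in 2.5 then states: "Pharmacokinetic parameters were similar to adults". For 11 children it gives Cmax, a half-life of 10.7 ± 1.8 days and a clearance of 0.196 ± 0.075 mL/h/kg. It gives no Cmin result and no adult figure alongside. On adults, section 2.3 says: "Half-life is 2-4 weeks, similar to other therapeutic antibodies".

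**The concern.** The aim asks a two-sided question, whether exposure is similar. The pre-specified rule asks a one-sided one, whether enough of six children clear a floor near the bottom of the adult range. Passing it cannot show similarity, and it cannot flag exposure that is too high. With summary statistics as the only other analysis, nothing in the plan estimates how child exposure compares with adult exposure or how precisely that is known.

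The similarity statement in 2.5 cannot be checked from the protocol. The quantity on which the gate turns is not reported, and the one listed parameter with an adult value elsewhere in the document lies outside that adult range. A primary aim could therefore be closed with a stronger conclusion than the analysis supports.

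**Working it through.** The documents state no operating characteristics for the gate, so there is no planned figure to reproduce.

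**1. The gate.** Inputs are the Table 2 percentiles (34 adults), the 10 mcg/ml threshold, and a proportional shift of adult troughs by a factor k (an assumption). Then p = P(adult Cmin ≥ 10/k), read by linear interpolation, and P(pass) = 6p⁵(1 − p) + p⁶. For k = 0.8 the adult value needed is 12.5. It lies between the 20th percentile (12.4) and the 25th (13.0), at 20 + 5 × 0.1/0.6 = 20.8. So p = 0.792 and P(pass) = 0.635.

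| Child:adult ratio k | 10/k | p | P(pass) |
|---|---|---|---|
| 1.0 | 10.0 | 0.924 | 0.93 |
| 0.9 | 11.1 | 0.881 | 0.85 |
| 0.8 | 12.5 | 0.792 | 0.63 |
| 0.7 | 14.3 | 0.701 | 0.42 |
| 0.5 | 20.0 | 0.395 | 0.04 |
| 1.5 | 6.7 | 1.00 | about 1.00 |

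At k = 0.8, the bracketing percentiles (p = 0.75 and 0.80) give 0.53 to 0.66. Lognormal and normal fits to Table 2 give 0.68 and 0.67. An observed 5 of 6 has a one-sided 95% exact lower bound of 0.42 for the true proportion, against 0.92 in the adults.

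**2. The 10 to 30 range.** In Table 2, 10 is at 5 + 5 × (10 − 8.9)/(11.0 − 8.9) = the 7.6th percentile, and 30 is at 90 + 5 × (30 − 28.6)/(31.2 − 28.6) = the 92.7th. The range therefore holds about 85% of individual adults. The interpolated 2.5th to 97.5th percentiles are about 7.9 to 34.7. A 95% CI for the adult mean (normal fit: mean 18.55, SD 6.97) is 18.55 ± 2.03 × 6.97/√34 = 16.1 to 21.0. Neither is 10 to 30.

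**3. Half-life.** Reading ± as an SD, the 95% CI for the child mean is 10.7 ± 2.228 × 1.8/√11 = 9.5 to 11.9 days. The adult range quoted is 14 to 28 days.

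**4. Exposure implied by the child means.** This is a rough one-compartment estimate.
- Volume = 0.196 × 24 × 10.7/ln 2 = 72.6 mL/kg.
- Starting level = 3000/72.6 = 41.3 mcg/ml.
- Day-14 level = 41.3 × 2^(−14/10.7) = 16.7 mcg/ml, against the adult median of 17.6.
- Decay from the reported Cmax of 63.2 (read as mcg/ml) gives 63.2 × 2^(−14/10.7) = 25.5.

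Both estimates are above 10.

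**5. Precision of a ratio.** The log SD from the Table 2 quartiles is ln(24.1/13.0)/1.349 = 0.458, assumed equal in children. The 90% CI factor is exp(1.645 × 0.458 × √(1/n + 1/34)). This is 1.30 for n = 11 and 1.17 for n = 85. The 85 is the section 11.1 enrollment: 13 in Part A plus 72 in Part B (10 + 10 + 11 + 10 + 12 + 10 + 1 + 8).

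**The case against.** The strongest reply is that the gate was never the analysis of the aim. It is a dose-selection check against under-exposure, it states only that conclusion, and it catches large shortfalls: at half the adult exposure it passes about 4% of the time. Section 11.1 also requires at least 6 children under 12 and 6 aged 12 or over to be evaluated for systemic exposure across Parts A and B, so the assessment is not confined to six children. Descriptive pharmacokinetics are common in phase 1/2 work, and Parts A and B are complete. All of this stands. It does not supply what is missing, because 11.1 gives patient numbers and no method of comparison, and 11.9 gives none either.

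Three stronger readings are tempting, and the documents do not support them.

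- A reader might infer that the half-lives contradict similar exposure. Half-life is not exposure, and it is not among the parameters named in 1.1 or 8.3.1. The adult 2 to 4 weeks follows a statement covering 0.1 to 10 mg/kg and carries no sample size or method. Child sampling in Appendix IIIA spans at most 14 days after a dose. The child clearance points to a trough near the adult median.
- A reader might infer that the similarity statement came from the 5-of-6 gate. Section 2.5 does not say so. It reports parameters for 11 children and cites an abstract whose adult comparators are not in the documents.
- A reader might infer that children are under-exposed. Nothing here shows that.

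**Conclusion.** The point holds as a gap in analysis and reporting. The primary exposure aim has no method that can show similarity. The gate supports only not-less, with pass probabilities of 0.93, 0.63 and 0.42 at exposure ratios of 1, 0.8 and 0.7, and about 1.00 at 1.5. These figures assume a proportional shift of Table 2. The 20% and 30% deficits are illustrative, since the documents define no margin; at 20% lower, other readings of the table give 0.53 to 0.68.

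The similarity statement in 2.5 is undocumented, which is different from wrong. No trough result is given, and the only parameter that can be compared is below the adult range quoted, while the rough trough estimate (16.7 against 17.6 mcg/ml) leans towards similarity. The 95% label on 10 to 30 mcg/ml does not match Table 2. None of this shows that the dose decision was mistaken.

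**What to change.** **Section 11.9.** Answer the aim with the child:adult geometric mean ratio of first-dose Cmin, against the Table 2 adults, with a 90% CI.
- Use the available Day 15 pre-dose samples (Appendix IIIA) from Part A and B patients under 18 years treated at 3 mg/kg. Section 4.1.1 admits patients up to 30 years to most Part B cohorts, so show older patients separately; pooling them would put adults in the child group.
- Add the proportion at or above 10 mcg/ml with an exact CI.
- Obtain the 34 individual adult values if possible, since the protocol prints only percentiles.
- Confirm that the adult sampling time matches a Day 15 pre-dose draw. One day at a 10.7-day half-life is 2^(−1/10.7) = 0.94, a 6% difference.

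Expect a 90% CI within a factor of about 1.30 with 11 children. More children will narrow it, but not to 1.17, which assumes that all 85 enrolled patients are children with usable samples. The documents do not say how many Part B patients were under 18.

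**Section 2.5.** Limit the gate's conclusion to not-less. Report the Part A Cmin results and the adult comparators behind the similarity statement, and note that the half-life is shorter than the adult range quoted in 2.3. Relabel 10 to 30 mcg/ml as roughly the 8th to 93rd percentile of individual adult values.

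**Cost.** A short analysis of samples the protocol already requires, some wording changes, and a stated conclusion that may be less favourable. Enrollment and dosing are unaffected.
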